8.6 Efficacy Assessments

Clinical assessments of the extent and severity of plantar lesions will be performed throughout the study.

Foot Health Status Questionnaire (FHSQ)

The purpose of this questionnaire is primarily to measure foot health related to foot function and quality of life. There are 19 questions regarding foot health and its impact with 4 subscales: foot pain, foot function, footwear and foot health. It has been shown to have excellent validity and ability to detect change in clinical trials and has demonstrated good reliability (Riskowski et al., 2011).

Epidermolysis Bullosa Disease Activity Score (EBDASI)

The EBDASI is a validated scoring system that objectively quantifies the severity of EB affecting the entire body. It has been designed to evaluate the response to new therapies for the treatment of EB. It was developed and validated many times over in the literature (Loh et al., 2014)

EBDASI feet score

Is a subsection of the EBDASI and objectively quantifies activity and damage levels relating to the feet only. Activity is graded according to size and number of lesions (blisters/erosions) in specific anatomical area. Damage is graded according to the presence/absence of the following signs: erythema, pigmentation, poikiloderma, atrophy, hyperkeratosis, scarring and milia.

Method of defect assessment

Tracing of affected wounds will be performed using Visitrak Digital Wound Assessment System. This is a portable device that provides accurate, reproducible data for tracking wound progress (See Figure 2).

Quality of life in Epidermolysis Bullosa (QOLEB)

QOLEB is a Quality of Life Questionnaire specifically designed for people with EB. The QOLEB can be used to identify everyday life occurrences negatively affected by EB. It assesses change in quality of life over time, an important measure when assessing the success of new treatments for EB (Frew et al., 2009).

Plantar Pressure Measurements

The Podotech Elftman foot pressure scanner uses 1600 electronic sensors incorporated into a thin mat to measure pressures at various points on the soles of the feet. This analysis can be performed while standing to get a static analysis or when walking to get a dynamic analysis. Peak pressures can be calculated and can correlate with areas of hyperkeratosis and changes in loading due to pain. A before and after assessment of participants feet using this device will give us insight into how hyperkeratosis has changed as well as

changes in loading and pain. This technology is extensively investigated in rheumatoid arthritis patients (Van der leeden et al 2008).

Fitbit Pedometer Mobility Measurements

Each enrolled study subject will receive a FitBit®/pedometer during their participation in the study to track their activity levels. This purchase will be made using our SPARK grant funding and be provided to subjects at no cost. Will add the information below to the consent and in Section 16.

The FitBit / pedometer will sync stats wirelessly to a deidentified premium account at www.fitbit.com/zip. An Excel form of the data will be downloaded on health protected computers every two weeks. FitBit pedometers have been demonstrated in the literature as reliable and accurate (Storm FA et al. Step Detection and Activity Recognition Accuracy of Seven Physical Activity Monitors. PLoS ONE, 2015).

Erythema score of soles of feet

An erythema score of a specified location on the soles of the feet will be obtained through use of Mexameter® MX 18 to detect any change in erythema at each study visit. This will be an objective measure of local skin irritation at the treatment site. This is an easy, quick and economical tool to measure erythema by reflectance. The instrument is worldwide established and used in many scientific studies.

Skin biopsies assayed for mTOR pathway inhibition

The skin biopsies are optional and will be assayed for transcriptional factors of mTOR pathway inhibition using Western blot / immunohistochemical methods (Transderm laboratory, Santa Cruz USA) e.g. determination of phosphoprotein inhibition included ribosomal protein S6, S6 kinase and/or eIF-4E binding protein. Tissue samples will be transferred to Transderm laboratory deidentified and without identifiable personal health information. A separate consent, and if applicable, assent form(s) will be used.

5-D Pruritus Scale

People with EBS can experience the aggravating symptom of itch. This validated tool will be utilized to assess the effect (if any) topical sirolimus has on this symptom (Elman et al., 2010)

8.7 Adverse Events (AE) and Serious Adverse Events (SAEs)

The investigator is responsible for detecting, documenting, and reporting events that meet the definition of an AE or SAE. AEs will be collected from the start of study treatment through the protocol-specified follow-up period.

Definition of an AE: Any untoward medical occurrence in a subject or clinical investigation subject, temporally associated with the use of a medicinal product, whether or not considered related to the medicinal product.

Note: An AE can therefore be any unfavorable and unintended sign (including an abnormal laboratory finding), symptom, or disease (new or exacerbated)

temporally associated with the use of a medicinal product. This also includes failure to produce expected benefits (i.e. lack of efficacy), abuse, or misuse.

A serious adverse event (SAE) is any untoward medical occurrence that:

- a. Results in death
- b. Is life-threatening
- c. Requires hospitalization or prolongation of existing hospitalization
- d. Results in disability/incapacity, or
- e. Results in a congenital anomaly/birth defect

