8.3 Primary outcome measures

1. Foot function utilizing the validated Foot Health Status Questionnaire (FHSQ) as a change from baseline to the end of each treatment.
2. Safety and tolerability of topical sirolimus 2% ointment (serum trough sirolimus levels, monitoring for adverse events).

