8.5 Safety Assessments

Safety and tolerability of the medication will be assessed at each visit through recording of adverse events, serious adverse events, evaluation of systemic absorption through measurement of trough sirolimus levels in serum, and additional safety laboratory tests listed below will also be performed.

Investigator assessment of local skin reaction (including increased erythema, edema, weeping/exudates, flaking/scaling/dryness, scabbing/crusting, and erosion/ulceration) will be assessed independently of other adverse effects.

Serum sirolimus levels

Trough serum sirolimus levels are a frequently run outpatient laboratory ELISA assay and will be performed at Stanford University at specific study visits from baseline.

Other Safety Laboratory Assessments

The clinical safety laboratory parameters will be assessed at each study visit. Laboratory tests may be repeated more often if clinically indicated.

All out-of-normal range laboratory values must be evaluated by the Investigator or subinvestigator as to whether they are clinically significant (i.e., require medical intervention or have clinical signs and/or symptoms). Abnormal clinical laboratory parameters that are considered clinically significant by the Investigator will be recorded on the Adverse Event (AE) Case Report Form (CRF) except Baseline visit. Clinically significant laboratory abnormalities noted from the Baseline visit will be recorded as medical history. The AE should be reported as a clinical diagnosis when possible. Laboratory tests will be performed at Stanford Children's Health clinics.

Urine Pregnancy Tests (UPT) will be performed at each scheduled visit on female subjects of childbearing potential starting at Baseline. If a UPT results in a positive test, the subject must be discontinued.

Sample management (collection, storage, shipping, etc...) will be done according to Stanford Clinical Laboratories standards and policies.

Clinical safety laboratories will include:

- Full blood count (CBC, Metabolic Panel, Liver function tests)
- Lipid panel profile
- Urinalysis
- Sirolimus trough (at specific study visits)

These will be performed at each scheduled study visit from screening/baseline visit (7 total), except for sirolimus trough.

Adverse Events (AE) and Serious Adverse Events (SAEs)

1. AE frequency, severity, and relationship to IMP.
2. Frequency of withdrawals due to treatment-related AEs.
3. Frequency of serious adverse events (SAEs)

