9.3 Treatment comparisons

The primary comparison of interest is between placebo and topical sirolimus 2% on foot function using the validated Foot Health Status Questionnaire.

Secondary comparisons of interest will be made between placebo and topical sirolimus 2% on the secondary outcome measures.

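### Section 8.7 counts lack of efficacy as an adverse event, which mixes the efficacy result into the AE component of the primary safety outcome

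*Combined protocol and SAP*

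**What the plan says.** Section 8.7 defines an AE broadly, as an untoward occurrence "temporally associated with the use of a medicinal product, whether or not considered related to the medicinal product". A note then extends the definition to signs, symptoms and disease that is new or has worsened, and adds: "This also includes failure to produce expected benefits (i.e. lack of efficacy), abuse, or misuse". The same section gives the investigator the duty to find, record and report whatever meets the definition. On timing it says: "AEs will be collected from the start of study treatment through the protocol-specified follow-up period".

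No other section removes lack of efficacy from the AE count, sets a threshold or time point for judging it, or asks for it to be shown separately. No rule assigns an AE to a treatment or period.

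Safety is Aim 1 (section 4.0) and the second of two primary outcomes in 8.3: "Safety and tolerability of topical sirolimus 2% ointment (serum trough sirolimus levels, monitoring for adverse events". The first AE summary listed in 8.5 is "AE frequency, severity, and relationship to IMP".

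**The concern.** One of the two treatments is vehicle only (7.1), and the trial hypothesis is that sirolimus is superior (9.1). If that is true, absence of benefit will be seen more often in vehicle periods. Followed as written, 8.7 turns those observations into AEs. The same fact is then counted twice: as efficacy, through the Foot Health Status Questionnaire (FHSQ), EBDASI feet score, defect area and 5-D itch scale, and again as safety.

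An AE frequency built this way is not a clean measure of harm. Extra toxicity on sirolimus could be offset, or more than offset, by lack-of-efficacy entries on vehicle. With 8 to 10 participants (5.1), each one is worth 10 to 12.5 percentage points (1/10 to 1/8), so a few entries can dominate the table.

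**Working it through.** **No plan figure to reproduce.** The documents give no AE rate, no rate of lack-of-efficacy recording and no sample size for safety. The calculation in 9.2 concerns foot function only and has no bearing here. All rates below are assumptions that show the mechanism and its range.

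**Model.** For one treatment period, let *p* be the probability of at least one true AE and *q* the probability that lack of efficacy is recorded as an AE. Assume that the two are independent.

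- P(any AE) = 1 - (1 - p)(1 - q)
- With the same *p* on both treatments, the spurious difference (sirolimus minus placebo) is (1 - p)(q_S - q_P).
- With the same *q* on both treatments, a true difference p_S - p_P appears as (p_S - p_P)(1 - q).

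**Equal true AE risk, p = 0.20 on both treatments**

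| q sirolimus / placebo | Sirolimus any AE | Placebo any AE | Difference |
|---|---|---|---|
| 0.5 / 0.5 | 1 - 0.8×0.5 = 60% | 1 - 0.8×0.5 = 60% | 0 |
| 0.4 / 0.6 | 1 - 0.8×0.6 = 52% | 1 - 0.8×0.4 = 68% | -16 points |
| 0.3 / 0.8 | 1 - 0.8×0.7 = 44% | 1 - 0.8×0.2 = 84% | -40 points |

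The last row corresponds to about 3.5 against 6.7 of 8 participants (8×0.44 and 8×0.84).

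**Sensitivity to p, from 0 to 0.4.** For q of 0.4/0.6 the spurious difference runs from 1.0×(-0.2) = -20 points to 0.6×(-0.2) = -12 points. For 0.3/0.8 it runs from 1.0×(-0.5) = -50 points to 0.6×(-0.5) = -30 points.

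**True excess on sirolimus, p = 0.40 against 0.20 (+20 points)**

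| q sirolimus / placebo | Sirolimus any AE | Placebo any AE | Apparent difference |
|---|---|---|---|
| 0 / 0 (lack of efficacy kept out) | 40% | 20% | +20 points |
| 0.5 / 0.5 | 1 - 0.6×0.5 = 70% | 1 - 0.8×0.5 = 60% | +10 points |
| 0.4 / 0.6 | 1 - 0.6×0.6 = 64% | 1 - 0.8×0.4 = 68% | -4 points |
| 0.3 / 0.8 | 1 - 0.6×0.7 = 58% | 1 - 0.8×0.2 = 84% | -26 points |

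Equal recording halves the visible excess. Unequal recording of the size assumed here reverses its sign.

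**Scale.** The dilution applies to the percentage with any AE. For the mean number of AEs, with at most one lack-of-efficacy entry per period, the shift is simply q_S - q_P. It is zero when recording is equal.

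**The case against.** **No such comparison is planned.** A reader might infer that a formal primary safety comparison is biased. The documents contain none. Section 9.3 states: "The primary comparison of interest is between placebo and topical sirolimus 2% on foot function using the validated Foot Health Status Questionnaire". It continues: "Secondary comparisons of interest will be made between placebo and topical sirolimus 2% on the secondary outcome measures". AE frequency is not among the secondary outcomes, and 9.1 states efficacy hypotheses only. This objection stands, and the point is limited to tabulations of AE frequency by treatment. Such a tabulation is the natural reading of AE frequency in a placebo-controlled trial, even without a test.

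**Most safety evidence is untouched.** A reader might also infer that Aim 1 cannot be answered. That goes too far. Trough sirolimus and the laboratory tests do not depend on the definition, and local skin reaction, including erosion and ulceration, "will be assessed independently of other adverse effects". The Mexameter erythema score (8.6) is likewise separate. With 8 to 10 participants, events can also be listed and read one by one. All of this stands. What suffers is the AE component.

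**Recording may be rare.** The sentence sits in a note on what an AE can be, and expected benefit is undefined. It does not follow that every non-responder will have an AE entered. This stands as a limit on size. It also means that entries would follow each blinded investigator's impression of response, which is itself an efficacy judgement. Blinding does not remove a shift caused by a real difference in efficacy.

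**The rates are assumed.** They are. With equal efficacy and equal recording there is no directional bias, so a fixed bias toward sirolimus cannot be claimed.

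**Conclusion.** The point holds for the AE component of primary outcome 2. The definition in 8.7 admits lack of efficacy, nothing elsewhere takes it out, and AE frequency is a listed safety summary.

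The direction is conditional. A real or perceived advantage of sirolimus, together with investigators who record as 8.7 directs, shifts AE frequency by treatment in favour of sirolimus. Equal efficacy and recording leave no directional bias, but shrink a true any-AE difference by the factor (1 - q).

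The size cannot be derived from the documents. Under the assumed 20% true risk, independence, and recording of 40%/60% to 30%/80% (sirolimus/placebo), the spurious any-AE difference is -16 to -40 points. It is 0 when recording is equal. The claim does not extend to a formal safety test or to the other safety measures.

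**What to change.** In 8.7 and on the AE form, record lack of efficacy under a separate code. State in 8.3 and 8.5(1) that entries with this code are excluded from the AE frequency and from primary outcome 2, and are reported on their own line by treatment. Present the remaining AEs by treatment at onset, and state where events that start in a washout are counted.

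Disease that is new or has worsened, including plantar worsening, should remain a reportable AE, and all serious AEs should be kept. It would be simpler to stop recording plantar changes already captured by the efficacy scales, but that could filter out drug-related harm: 8.7 now counts exacerbated disease as an AE, and 2.2 lists delayed wound healing among the effects of systemic sirolimus. A separate code loses no data.

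The cost is one extra code, one table line and short edits to 8.3, 8.5 and 8.7. The downside is small: the investigator must separate absence of benefit from worsening, and a short definition of each on the form would help.

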2.2 Sirolimus

Sirolimus binds to immunophilin FK506 binding protein-12 and creates a complex that inhibits the activation of mTORC1 that leads to decreased translational initiation. Consequently, sirolimus has shown to decrease overall protein synthesis by 20% and cause cell cycle arrest in G1 phase. (Castedo et al., 2001) Other effects of sirolimus include apoptosis, inhibition of T-cell activation and reduced expression of specific proteins involved in angiogenesis and lymphangiogenesis, specifically hypoxia inducible factor-1a (HIF-1a) and vascular endothelial growth factor (VEGF). (Guba et. al 2002)

Systemic use of sirolimus is associated with side effects that include opportunistic infection, mucositis, hypercholesterolemia, decreased renal function, elevation in liver transaminases, thrombocytopenia, neutropenia, and delayed wound healing. Minor adverse cutaneous events of systemic therapy include acne like eruptions, edema, and nail disorders. mTOR inhibitors in topical preparations show promise as an ideal delivery system to minimize systemic adverse effects in the treatment of dermatological disease.

Topical formulations of sirolimus are being used off-label in a variety of dermatological diseases (see Table 1) (Fogel et al, 2015). Formulations are mostly crushed sirolimus from tablet compounded with petrolatum to form an ointment, with a few studies utilizing the commercially available oral sirolimus solution (1mg/ml). Most of the topical formulations were found to have no local adverse effects, with irritation being more common using the aqueous solution. In all cases the systemic level of sirolimus was less than 2ng/ml that is below the standard serum levels required for immunosuppression (5-15 ng/ml). Treatment duration and frequency varied according to condition.

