10.2 Regulatory and ethical considerations

The study will be conducted in accordance with ICH Good Clinical Practice, and the ethical principles that are outlined in the Declaration of Helsinki 2008.

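### The SAE definition in section 8.7 is a closed list of five outcomes with no important-medical-event criterion, so some serious toxicities that do not lead to admission are left out of the SAE frequency in section 8.5

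*Combined protocol and SAP*

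**What the plan says.** Section 8.7 defines seriousness by outcome. After the lead-in "A serious adverse event (SAE) is any untoward medical occurrence that" come five items:

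- a: death
- b: "Is life-threatening"
- c: "Requires hospitalization or prolongation of existing hospitalization"
- d: "Results in disability/incapacity, or"
- e: a congenital anomaly or birth defect

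Section 8.8 (Pregnancy) follows directly.

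Section 8.5 lists three adverse-event measures: the frequency, severity and relationship of AEs; withdrawals due to treatment-related AEs; and the frequency of SAEs. It also requires every out-of-range laboratory value to be judged for whether it is "clinically significant (i.e., require medical intervention or have clinical signs and/or symptoms". After baseline, values judged so go on the AE form.

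Section 2.2 gives the background on harm: "Systemic use of sirolimus is associated with side effects that include opportunistic infection, mucositis, hypercholesterolemia, decreased renal function, elevation in liver transaminases, thrombocytopenia, neutropenia", with delayed wound healing also listed. Safety is Aim 1 in section 4.0 and the second primary outcome in section 8.3. Section 10.2 adds a general commitment: "The study will be conducted in accordance with ICH Good Clinical Practice".

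**The concern.** The harms that section 2.2 names for systemic sirolimus include several that can be medically important and still be managed without a hospital bed, such as an opportunistic infection, a low neutrophil or platelet count, or impaired kidney or liver function. Section 8.5 already recognises laboratory changes that call for intervention. Nothing in 8.7 lets the investigator class such a change as serious on that ground alone.

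What is at stake is the meaning of the SAE frequency in a trial whose first aim is safety. A report of no SAEs would normally be read as no serious toxicity. Under the 8.7 wording it would mean only that none of five specified outcomes occurred.

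**Working it through.** The plan gives no figure to reproduce, because the point concerns the wording of a definition. The check has four steps.

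**Step 1: is the list closed?** The lead-in has no wording such as *including* or *for example*. The *or* at the end of item d makes item e the last alternative. The list therefore has five criteria, and none concerns medical importance.

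**Step 2: does another section add a criterion?** Section 8.5 counts SAEs but does not define them. It sends clinically significant laboratory changes to the AE form, with no rule that raises them to SAE. Section 10.2 is a general statement and supplies no definition. The schedule of events has an SAE row at every contact but no definition. No list of events of special interest appears in the available text.

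**Step 3: apply the list.** Take an infection or neutropenia that needs intervention and is managed without admission, and vary its other features.

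| Event, managed without admission | a | b | c | d | e | Counted as SAE? |
|---|---|---|---|---|---|---|
| Life-threatening | no | yes | no | no | no | yes, through b |
| Leaves disability or incapacity | no | no | no | yes | no | yes, through d |
| Needs intervention; neither of the above | no | no | no | no | no | no |

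The gap is the third row. Such an event enters the AE frequency, with severity and relationship, but not the SAE frequency.

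**Step 4: are these harms relevant to a topical product?** Two statements in the protocol bear on this:

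- Section 2.2 says systemic levels were below 2 ng/ml in every case reviewed and gives 5-15 ng/ml as the immunosuppressive range.
- Table 1 includes a series of 19 patients on 0.1%-1% ointment. In 17 the drug was undetected, one had 5 µg/L and one had 8 µg/L.

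Since 1 µg/L equals 1 ng/ml, the two measured values are 5 and 8 ng/ml. Both lie inside the 5-15 ng/ml range, and both contradict the statement that all levels were below 2. Systemic exposure with topical use is therefore documented in the protocol's own table, in 2/19 = 10.5% of that series. The trial uses 2%, above any concentration in Table 1, and plans trough levels to look for absorption.

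**Size.** Section 5.1 plans 8-10 participants. One participant with a third-row event, and no other SAE, would change the SAE frequency from 0/8 to 1/8 = 12.5%, or from 0/10 to 1/10 = 10%.

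**The case against.** The strongest reply is that nothing is hidden. Section 8.5 reports the severity and relationship of every AE, and in a trial of 8-10 people a severe, related neutropenia would be plain to any reader of the AE listing. Section 8.3 describes the safety outcome through trough levels and AE monitoring and does not name SAE frequency. This stands, and it limits the point to a label and a count. It does not remove the point, because SAE frequency is still a stated measure and the available text names no severity scale that could replace a seriousness flag.

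A second reply is that section 2.2 describes systemic use, and the footnote to Table 1 says irritation was the only side effect reported in any of the series. That is fair: the table shows exposure, not systemic toxicity, and gives no rate for the events in question.

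A third is that no document here requires an important-medical-event criterion. That is also true, and the general commitment in 10.2 is not used here as proof of one. The case rests on the protocol's own named harms, its own class of laboratory changes needing intervention, and its safety aim.

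Three stronger readings are tempting, and the documents do not support them.

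- *A toxicity managed without admission can never be an SAE.* Items b and d apply without admission.
- *Such events would not be handled as serious during the trial.* The available text ties no action to SAE status, and section 8.7 gives the investigator the same duties for AEs and SAEs. For infection, sections 5.3 and 5.4 together already require withdrawal when a participant comes to meet an exclusion criterion, and one of those covers serious infection that could pose a safety risk. The contents list an IDMC section (10.4) that is not in the available text, so nothing can be inferred from it either way.
- *Confidence intervals show a large impact.* The exact 95% intervals are 0-36.9% for 0/8 and 0.3-52.7% for 1/8, and 0-30.8% for 0/10 and 0.3-44.5% for 1/10. Each pair overlaps almost entirely. They show how little a rate can say at this sample size under either definition.

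**Conclusion.** The point holds in a limited form. As written, section 8.7 leaves out of the SAE frequency any important toxicity that is not fatal, life-threatening or disabling, does not lead to admission and is not a birth defect. The event remains in the AE data with severity and relationship. The loss is one classification and one count within a primary safety outcome; a single affected participant would be worth 10 to 12.5 percentage points of SAE frequency. The documents give no probability of such an event, so no expected effect can be stated.

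The conclusion assumes that the five items are applied literally and that no further SAE criterion stands in text that was not available. It is an inexpensive improvement to the safety reporting and does not affect the efficacy comparison.

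**What to change.** Add a sixth item to section 8.7, for example: *f. Is, in the investigator's medical judgement, an important medical event that may jeopardise the participant or require intervention to prevent one of the outcomes in a-e.* Move the closing *or* to the end of item e. State in section 8.5 that SAE frequency is reported on this definition.

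The cost is one protocol line and one CRF item, with no change to treatment, visits, sample size or efficacy analysis. The SAE count may be slightly higher, and item f depends on investigator judgement. That judgement should be made and recorded while the investigator is blinded. Separately, the statement in section 2.2 on systemic levels and the two values in Table 1 must be reconciled.
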